6. STUDY DESIGN

a. Overall design

This is an open label, randomized, phase 3 study designed to compare romiplostim plus dexamethasone vs dexamethasone alone in terms of sustained response off any ITP treatment in adult subjects (≥18 years old) with newly diagnosed of ITP.

According to the International Working Group assessment [1] patients will be screened for study participation. Subjects who meet eligibility criteria will be enrolled. Once eligibility is confirmed, patient will be randomized, Randomization will be stratified by center with a 1:1 allocation using random block sizes, to receive dexamethasone 40 mg daily x 4 days only in the first cycle and subcutaneous romiplostim weekly for up to 12 months (ROM + DEX arm) or dexamethasone 40 mg daily x 4 days for up to 3 cycles every 14 to 28 days (DEX arm).

The monitoring will be the same in both arms with slight differences to allow for dose adjustments of romiplostim:

- In the ROM + DEX arm, patients will be reviewed weekly for 8 weeks (56 days). After week 8, patients will be reviewed every 2 weeks (14 days) for 8 additional weeks and then monthly until week 52 (365 days) from randomization.
 - o If romiplostim dose should be modified, patients will be reviewed weekly until a stable dose of romiplostim is reached for at least 4 weeks (28 days). After that, patients will go on with visits every 2 weeks (14 days) for 8 weeks and then monthly until Week 52 (365 days) from randomization.
- In the DEX arm, patients will be reviewed weekly until the completion of dexamethasone cycles and for a minimum of 8 weeks (56 days). After that,

every 2 weeks (14 days) for 8 additional weeks and then monthly until Week 52 (365 days) from randomization.

The following assessments will be done in these visits: platelets count, bleeding score, number and characteristics of bleeds, adverse events, study medication, rescue medication and concomitant medication, HRU associated with the ITP or its treatment and lost productivity (days of absentee in scholarship or work and presentism).

Quality of life will be evaluated at Day 1 (the day of administration of the first dose), Month2 (Day 60), Month 6 (Day 180) Month12 (Day 365) and End of study Visit (visit 12 months after the last dose of study treatment). See Study schedule for more details.

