- To compare the difference between study arms in the proportion of patients with adverse events (AEs), including serious adverse events (SAEs) and laboratory safety parameters. AEs will be graded according to National Cancer Institute Common Terminology Criteria for Adverse Events (CTCAE) version 5.0. Bleeding events will be carefully monitored.
- To compare the difference between study arms in the mean change in patients' bleeding from screening to Day 1, to Week 8, Week 12, Month 6,

Month 12 and End of study Visit (visit 12 months after the last dose of study treatment) with the ITP-bleeding assessment tool in both arm.

- To compare the difference between study arms in the mean change in patients' quality of life from baseline Day 1, (the day of administration of the first dose of study medication) to 2 (week 8), 6 months (Day 180), 12 months (Day 365) and End of study Visit (visit 12 months after the last dose of study treatment) assessed with SF-36 v2, FACIT-F and ITP-PAQ in both arm.
- To describe and compare the difference between study arms in mean of healthcare resources use (HRU) from treatment initiation to end of study (outpatient visits and home health care, hospitalizations and emergency visits, diagnostic procedures, pharmacological and non-pharmacological treatments and HRU related to management of adverse drug reactions) and loss of productivity (number of days of absenteeism from school or work and associated cost).

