Each subject who enters into the screening period for the study (when the subject signs the informed consent) will receive a unique subject identification number before any study-related activities/procedures are performed. The subject identification number will be assigned by the eCRF. This subject identification number will be used to identify the subject throughout the clinical study and must be used on all study documentation related to that subject.

Subjects who are determined not eligible after screening must be screen-failed in the eCRF and the reason for the screen failure provided.

Upon confirmation of eligibility, the site staff will use the eCRF to randomise a subject. Randomization of the patient is authorized until 72 hours after signing the informed consent. Randomization will be stratified by center with a 1:1 allocation using random block sizes to receive:

- Dexamethasone 40 mg daily x 4 days only in the first cycle and subcutaneous romiplostim weekly (ROM + DEX arm) for up to 12 months (365 days).
- Dexamethasone 40 mg daily x 4 days for up to 3 cycles every 14 to 28 days (DEX arm).

The investigator is responsible to document the decision to enroll the patient into the study and will note and date the information in the subject's medical record and in/on the enrolment CRF. Subjects will be considered enrolled upon randomization in the eCRF. The subject identification number must remain constant throughout the entire clinical study.

Romiplostim will be sent to the site upon subject screening.

d. Blinding procedures

Not applicable. Open label study.

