Study time point	Days -28 to -1	Day 1	Weekly visits until Week 7	Week 8	Weekly or biweekly visits until Week 14 ¹¹	Week 16 and week 20	Week 24 (Month 6)	Monthly visits until Month 11	Month 12	Monthly visits until Month 17 ¹²	Month 18 ¹²	Unscheduled visit
			±1 days	±1 days	±1 days	±3 days	±7 days	±3 days	±7 days	±7 days	±7days	
Eligibility criteria	Х	Х										
Informed consent ¹	Х											
Medical history ³	Х											
Demographics ²	Х											
Pregnancy test ⁴	Х											
Randomization		Х										
Vital signs ⁵	Х	Х	Х	Х	X ⁵	Х	Χ	Х	Х	X	Х	X
Physical examination ⁶	Χ	Х	X ⁶	Х	X _e	Х	Х	Х	Х	Х	Х	X
Laboratory tests ⁷	Χ	Х	Х	Х	Х	Х	Х	Х	Х	X	Х	Х
WHO Bleeding score	Х	Χ	Х	Χ	Х	Х	Χ	Х	Х	X	X	X
HRU and loss of productivity8		Χ	X	Χ	X	Χ	Χ	X	Χ	X	Χ	
Quality of life questionnaires:9 SF36, FACIT, ITP PAQ		Χ		Χ			X		Χ		Χ	
ITP-BAT ¹⁰	Х	Χ		Χ	X ¹⁰		Χ		Х		X	
ITP medication		Χ	Х	Х	Х	Х	Χ	Х	X			
Rescue medication		Х	Х	Х	Х	Х	Х	Х	Х			Х
Concomitant medication		Χ	Х	Χ	X	Х	Χ	Х	X	X	Χ	X
AEs/Bleeding event reporting//splenectomy		Х	Х	Х	Х	Х	Х	Х	Х	Х	Х	Х

- 1. Informed consent must be signed and dated prior to any study-related procedure and before any data is recorded in the CRF.
- 2. Demographic data collection including sex, age, and ethnicity.
- 3. Medical history includes all information related to a new diagnosis of ITP and bleeding events history.
- 4. The pregnancy test at screening will be conducted 72 hours before first dose of study treatment.
- 5. Vital signs includes respiratory rate, body temperature, blood pressure, and pulse rate. They must be measured every week until week 8, then every 4 weeks.
- 6. Physical examination will be performed as per standard of care. Physical measurements include height (at screening) and weight (at screening, baseline and from then on every 4 weeks+/- 1 week). There shall be no dose adjustments until changes of 10% or more in weight.
- 7. Complete blood counts with differential, blood chemistry profiles (serum creatinine, ALT, AST, GGT, K, Na, LDH) and platelet counts.
- 8. HRU and loss of productivity shall be measured monthly.
- 9. Quality of life (SF36 v2, FACIT-F and IPT-PAQ) will be evaluated at Day 1, week 8, Month 12 and End of study Visit (visit 12 months after the last dose of study treatment).
- 10. ITP-BAT will be evaluated to screening, Day 1, Week 8, Week 12, Month 6, Month 12 and End of study Visit (visit 12 months after the last dose of study treatment).

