- Quality of life measures using the SF-36 v2, FACIT-F and ITP-PAQ will be analysed. Change from baseline Day 1, (the day of administration of the first dose of study medication) to Week 8, Month6 (Day 180), Month12 (Day 365) and End of study Visit (visit 12 months after the last dose of study treatment) of SF-36 v2, FACIT-F and ITP-PAQ total score and each dimension score of SF-36 v2, FACIT-F and ITP-PAQ will be calculated. Both the change of scores and the scores at every assessed time point will be reported using the mean, median, standard deviation, min, max, Q1 and Q3.Student's t test will be used to compare the scores between treatment arms at different time points. Paired Student's t test will be used to evaluate the change from baseline at different time points within each treatment arm.
- The sum of all worst grades within each domain from the ITP-BAT questionnaire will be calculated and described at every assessed time point using the mean, median, standard deviation, min, max, Q1 and Q3.Student's t test will be used to compare the scores between treatment arms at different time points. Also, the change from baseline to Day 1, Week 8, Week 12, Month6 (Day 180), Month12 (Day 365) and End of study Visit (visit 12 months after the last dose of study treatment) of the sum of all worst grades within each domain from the ITP-BAT questionnaire will be calculated and described at every assessed time point using the mean, median, standard deviation, min, max, Q1 and Q3. Paired Student's t test will be used to evaluate the change from baseline at different time points within each treatment arm.
- Health resources use (HRU) associated with the ITP from treatment initiation (outpatient visits and home health care, hospitalizations and emergency visits, diagnostic procedures, pharmacological and non-pharmacological treatments and HRU related to of adverse drug reactions) and loss of productivity (number of days of absenteeism from school or work) will be summed up along the study and described using the mean, median, standard deviation, min, max, Q1 and Q3. Student's t test will be used to compare the scores between treatments.

In all hypothesis testing, p<0.05 will be considered statistically significant. No adjustments for multiplicity will be done. Since the amount of analysis of secondary objectives is numerous, results of the secondary endpoints should be considered exploratory and interpreted with caution.

ii. Secondary Safety evaluations

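### The only quality-of-life baseline in this open-label trial falls on the randomisation and first-dose day, and nothing requires it to be completed before the arm is known

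*Protocol*

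**What the plan says.** - **Timing.** Section 6.a: "Quality of life will be evaluated at Day 1 (the day of administration of the first dose". The later assessments are at Month 2, Month 6, Month 12 and the End of study Visit.
- **Schedule.** In both arm tables of Table 3, the row "Quality of life questionnaires:9 SF36, FACIT, ITP PAQ" has its first mark at Visit 1 (Baseline, Day 1) and none at screening. Randomisation is marked in the same Visit 1 column. Footnote 9 says the questionnaires "will be evaluated at Day 1, week 8, Month 12 and End of study Visit". It leaves out the Month 6 assessment that the table marks, but it agrees that Day 1 comes first.
- **Outcome.** Section 6.c names the between-arm difference in mean change in "quality of life from baseline Day 1, (the day of administration of the first dose of study medication"), and section 1.j does the same.
- **Analysis.** Section 11.e.i computes "Change from baseline Day 1, (the day of administration of the first dose of study medication) to Week 8, Month6 (Day 180") and the later time points.
- **Allocation and blinding.** Section 7.c: "Upon confirmation of eligibility, the site staff will use the eCRF to randomise a subject". It does not mention the questionnaires. Section 7.d on blinding: "Not applicable. Open label study".

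**The concern.** Randomisation makes the arms comparable for anything measured before allocation is known. A self-report given after the patient learns the arm loses that protection. The two arms look very different to a patient: weekly injections for up to 12 months after one steroid course, against up to three four-day steroid courses. ITP-PAQ includes Fear, Bother and Psychological domains, where a reaction to the allocation is plausible.

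The same Day 1 value is subtracted from every later score, so a disturbed baseline would enter the mean change at Week 8, Month 6, Month 12 and End of study. No later analysis can recover a baseline that was collected too late. The order of procedures at Visit 1 is an instruction to sites and belongs in the protocol and its schedule, not in a statistical analysis plan.

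**Working it through.** The plan has no quality-of-life figure to reproduce. Its one sample-size calculation (63 per arm) concerns the primary endpoint and has no bearing here. The check is a reading of the sections side by side, followed by the algebra of a change score.

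**Step 1: Can a compliant site collect the baseline after disclosure?**
- Sections 6.a, 6.c and 11.e.i tie the baseline to the day of the first study dose.
- Assigned study medication can be given only after randomisation, so in an open-label trial the arm is known at some point on or before that day.
- Table 3 puts randomisation and the first questionnaires at the same visit and gives no order within it.
- Section 7.c and the randomisation paragraph under Study Assessments and Procedures set conditions for randomising: eligibility confirmed, within 72 hours of consent, and at most three prior in-hospital dexamethasone doses. Completed questionnaires are not among them.

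So the sequence randomise, dose, then questionnaires is allowed. The sequence questionnaires, then randomise is also allowed.

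**Step 2: Is there an earlier quality-of-life value to fall back on?** No. ITP-BAT is collected at screening, and sections 1.j and 6.c run its change from screening. SF-36v2, FACIT-F and ITP-PAQ have no screening mark.

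**Step 3: What would a shift do?** Let:
- p = the proportion of patients who answer after learning their arm (taken as equal in both arms);
- d = the mean between-arm difference that this knowledge produces in their Day 1 scores;
- f = the between-arm difference from the same reaction still present in follow-up scores.

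Then:

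expected between-arm difference in mean change = true effect + f − p × d

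- If p = 0, the term p × d vanishes, and the baseline adds no bias. The fix secures this case.
- If p > 0 and the reaction has faded by follow-up (f = 0), the bias is −p × d at each time point.
- If the reaction persists in full (f = p × d), it cancels in the change.

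The documents give no value for p, d or f, so no size can be computed. The term f belongs to any open-label follow-up and does not come from the baseline timing.

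**Step 4: Which analyses use the baseline?** Between-arm mean change (sections 1.j and 6.c) and the within-arm paired t tests (section 11.e.i) do. The between-arm Student's t test in section 11.e.i is described as a comparison of scores at each time point. At follow-up visits that comparison does not involve Day 1. The primary endpoint, built on platelets, ITP treatment and bleeding after cessation, does not either.

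**The case against.** The strongest reply is that this is an unstated order and not an error. The protocol fixes a day, not a moment after the dose. Visit 1 is labelled Baseline, eligibility is checked there too, and randomisation follows that check, so there is room for the questionnaires first. Sequence within a visit is often left to a study manual, and section 12.f refers to one that is not available here. This stands in part. A reader might infer that the protocol places the baseline after allocation, and the text does not say so. It neither requires nor rules out completion beforehand. What remains is that the chosen anchor, the first-dose day, does not protect the measurement.

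Four further limits stand:
- **Recall.** The protocol describes a past-week window for FACIT-F and a four-week window for ITP-PAQ. On Day 1 these cover almost entirely time before allocation, which dampens any reaction. The protocol gives no recall window for SF-36v2.
- **Size.** It is tempting to assume a shift in standard deviations and express it as a share of a detectable effect. Nothing in the documents supports a value. Such a figure would also assume that every patient answers after disclosure and that the reaction is gone by follow-up.
- **Scope.** A reader might extend the point to every change score in the trial. ITP-BAT has a screening value, so it is not affected in this way.
- **Stakes.** Section 11.e.i says secondary results are exploratory and are to be read with caution.

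**Conclusion.** The point holds in a limited form. The only baseline for SF-36v2, FACIT-F and ITP-PAQ may be given by some patients who know their arm, and this can bias the mean change from Day 1. The size is unknown and may be nil. It depends on how many patients answer after disclosure, how strongly they react, and whether the reaction fades, and the documents address none of these. The protocol does not contradict itself on the order. The conclusions on the primary endpoint and on follow-up scores are not in question. This is a free improvement to an exploratory outcome.

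**What to change.** In section 6.a and Table 3 (both arms), state that SF-36v2, FACIT-F and ITP-PAQ are completed after consent and before the eCRF randomisation is run. Record the completion time so that the order can be verified. For patients already enrolled, report completion relative to randomisation where it is known.

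The cost is a change of order within an existing visit and one recorded time. No visit, instrument or patient is added, and the sample size does not change.
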